9.7.1.3 Subject Disposition

The number (percentage) of subjects who completed the study treatment/study and discontinued from the study treatment/study and reasons for discontinuation will be provided.

9.7.1.4 Demographic and Other Baseline Characteristics

Demographic and other baseline characteristics will be summarized for each cohort in Phase 2 as well as by dose level in Phase 1 if appropriate. Demographic and baseline variables include, but are not limited to age, sex, race, Lansky score, and Karnofsky score.

9.7.1.5 Prior and Concomitant Therapy

All investigator terms for medications recorded in the CRF will be coded to an 11-digit code using the World Health Organization Drug Dictionary (WHO DD). The number (percentage) of subjects who took prior and concomitant medications will be summarized, using Anatomical Therapeutic Chemical (ATC) class and WHO DD preferred term. Prior medications will be defined as medications that started before the first dose of study drug. Concomitant medications will be defined as medications that (1) started before the first dose of study drug and were continuing at the time of the first dose of study drug, or (2) started on or after the date of the first dose of study drug or started up to 28 days after the subject's last dose. All medications will be presented in subject data listings.

9.7.1.6 Efficacy Analyses

Data cutoff for the primary study analysis in Phase 2 will occur when all evaluable subjects have completed at least 4 treatment cycles and, if applicable, a confirmatory scan has been performed (in case of a PR or CR at Week 16), or have discontinued study treatment early.

The following are evaluability criteria for objective response and non-target disease response analysis:

- **Evaluable for objective response:** Only those subjects who have measurable disease present at baseline and have their disease re-evaluated at post-baseline visits will be considered evaluable for objective response. These subjects will have their response classified according to RECIST 1.1 (for Ewing sarcoma/pPNET and rhabdomyosarcoma) or RANO (for HGG).
- **Evaluable for non-target disease response:** Subjects who have lesions present at baseline that are evaluable but do not meet the definitions of measurable disease and have had their disease re-evaluated at post-baseline visits will be considered evaluable for non-target disease. Subjects with only non-target disease will be summarized by their best overall response. The response will be classified according to RECIST 1.1 defined categories for subjects with non-target disease only.

9.7.1.6.1 PRIMARY EFFICACY ANALYSIS

Phase 1

The study will utilize the rolling 6 design. The primary objective of Phase 1 is to determine the MTD and to establish the RP2D.

Phase 2

The primary efficacy endpoint in Phase 2 is ORR at 16 weeks. Objective responses will count only confirmed CR and PR. Estimated ORR and its exact 95% CI using the Clopper-Pearson method will be presented.

9.7.1.6.2 SECONDARY EFFICACY ANALYSES FOR PHASE 1 AND PHASE 2

The secondary efficacy endpoints will be ORR at the time of data cutoff, DCR, CBR and DOR. These endpoints in Phase 1 will be summarized if appropriate and listed by dose level, and ORR will be based on only subjects with measurable disease at screening/baseline. For Phase 2, the ORR, DCR and CBR will be provided with exact 95% CIs using the Clopper-Pearson method. The DOR will be analyzed using Kaplan-Meier approach among the responders (CR or PR). If a subject had no record of disease progression or did not die before the data cutoff date, or before early discontinuation (including discontinuations due to toxicity, undocumented clinical progression, change of cancer treatment, or decreasing performance status), then the subject will be censored at the last available tumor assessment.

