- **Evaluable for non-target disease response:** Subjects who have lesions present at baseline that are evaluable but do not meet the definitions of measurable disease and have had their disease re-evaluated at post-baseline visits will be considered evaluable for non-target disease. Subjects with only non-target disease will be summarized by their best overall response. The response will be classified according to RECIST 1.1 defined categories for subjects with non-target disease only.

Primary Efficacy Analysis

Phase 1:

The study will utilize the rolling 6 design. The primary objective of Phase 1 is to determine the MTD and to establish the RP2D.

Phase 2:

The primary efficacy endpoint in Phase 2 is ORR at 16 weeks. Objective responses will count only confirmed CR and PR. Estimated ORR and its exact 95% confidence interval (CI) using the method of Clopper and Pearson will be presented.

Secondary Efficacy Analyses for Phase 1 and Phase 2

The secondary efficacy endpoints will be ORR at the time of data cutoff, DCR, CBR and DOR. These endpoints in Phase 1 will be summarized if appropriate and listed by dose level, and ORR will be based only on subjects with measurable disease at screening/baseline. For Phase 2, the ORR, DCR and CBR will be provided with exact 95% CIs using the method of Clopper and Pearson, and the DOR will be analyzed for responders using Kaplan-Meier approach.

Pharmacokinetic, Pharmacodynamic, Pharmacogenomic, and Other Biomarker Analyses

Pharmacokinetic Analysis

Lenvatinib and everolimus concentration versus time data will be tabulated and summarized and graphically presented.

Plasma concentrations of lenvatinib from the intense sampling in Phase 1 will be used to determine the following PK parameters: area under the plasma concentration time course profile (AUC), maximum observed concentration (C_{max}), and time from dosing to the maximum observed concentration (T_{max}). Other PK parameters may be determined as data permit.

For both lenvatinib and everolimus, data from both Phase 1 and 2 of the study will be pooled with available data from other studies and subjected to population PK analysis. For each drug, the PK model will be parameterized in terms of clearance and volume of distribution. Details of the population PK analysis will be provided in a separate analysis plan.

Pharmacodynamic, Pharmacokinetic/Pharmacodynamic, Pharmacogenomic, and Other Biomarker Analyses

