8 STUDY OBJECTIVES

8.1 Primary Objectives

- **Primary Objectives for Phase 1**
 - a. To determine maximum tolerated dose (MTD) and recommended Phase 2 dose (RP2D) of lenvatinib administered in combination with everolimus, once daily to pediatric subjects with recurrent/refractory solid tumors.
 - b. To describe the toxicities of lenvatinib administered in combination with everolimus once daily to pediatric subjects with recurrent/refractory solid tumors.
- **Primary Objective for Phase 2**
 - a. To estimate the antitumor activity of lenvatinib in combination with everolimus in pediatric subjects with selected recurrent/refractory solid tumors including Ewing

sarcoma/pPNET, rhabdomyosarcoma, and HGG using objective response rate (ORR) at Week 16 as the outcome measure.

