Phase 2 Cohorts 1 to 3 will use a 10+10 Simon's optimal 2-stage design for each cohort; 10 evaluable subjects will be enrolled to each stage. The Sponsor will closely monitor enrollment to ensure that at least 50% of subjects enrolled in each cohort are <18 years of age at the time of informed consent. The primary outcome measure for Ewing sarcoma/pPNET, rhabdomyosarcoma, and HGG will be ORR (complete or partial response) at 16 weeks. If there are no responses among the 10 subjects in Stage 1, then the enrollment to that disease cohort will stop and conclude that the lenvatinib/everolimus combination therapy does not elicit a response in that disease cohort. If there is at least 1 response in the first stage, then the second stage will enroll 10 additional evaluable subjects. If there are 2 or fewer responses among the 20 evaluable subjects, then lenvatinib/everolimus combination therapy will be declared a failure for that disease cohort. Subjects will meet the criteria for being evaluable for an objective response if they have measurable disease present at baseline and at least 1 post-baseline efficacy assessment, unless they have discontinued prior to the first efficacy assessment due to progressive disease. Subjects who are not evaluable for objective response will be replaced.

The Treatment Phase for each subject in Phase 2 ends after completing 4 cycles of treatment unless subject discontinues early. Those subjects who discontinue study treatment before completing 4 cycles transition to the Off-treatment Visit. Those who complete 4 cycles will transition to the Extension Phase. Study treatment and tumor assessments will continue during the Extension Phase.

Dosing Nomogram

The dose nomogram in [Table 3](#) provides the dose of lenvatinib to be administered for BSA increments starting from 0.6 m². BSA must be calculated on Day 1 of each cycle based on the subject's current height and body weight. The actual dose to be administered is rounded to the nearest whole number. The total lenvatinib dose is capped at 18 mg daily (Dose Levels -1 and 1), and at 24 mg (Dose Levels 2 and 3).

Table 3 Total Lenvatinib Dose (mg): Body Surface Area (m²) * Dose Level (mg/m²)

Lenvatinib Dose Levels							
8 mg/m ² Everolimus 3.0 mg/m ² Dose Level -1		11 mg/m ² Everolimus 3.0 mg/m ² Dose Level 1		14 mg/m ² (Everolimus 3.0 mg/m ²) Dose Level 2		14 mg/m ² (Everolimus 4.5 mg/m ²) Dose Level 3	

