9.7.3 Interim Analysis

For each disease cohort (Ewing sarcoma/pPNET, rhabdomyosarcoma and HGG) in Phase 2, there will be 1 futility analysis: this is planned for after the first 10 evaluable subjects have completed at least 4 treatment cycles and, if applicable, a confirmatory scan has been performed (in case of a PR or CR at week 16), or have discontinued study drug early (before Week 16). At the futility analysis, if there are no responders (CR/PR), then the enrollment for that cohort will be discontinued for lack of efficacy. If 1 or more responses are observed, the accrual will continue.

Independent data monitoring committee (IDMC)

Safety monitoring will be conducted by an independent data monitoring committee (IDMC). The frequency of safety reviews will be defined in the IDMC charter. Minutes from the open meetings of the IDMC will be provided if requested by regulatory agencies. The function and membership of the IDMC will be described in the IDMC charter.

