Phase 2 Cohorts 1 to 3 will use a 10+10 Simon's optimal 2-stage design [Simon, 1989] for each cohort; 10 evaluable subjects will be enrolled in Stage 1 for each cohort. The primary outcome measure for Ewing sarcoma/pPNET, rhabdomyosarcoma, and HGG will be ORR (complete or partial response) at 16 weeks. If there are no responses among the 10 subjects in Stage 1, then the enrollment to that disease cohort will stop for futility. If there is at least 1 response in the first stage, then the second stage will enroll 10 additional evaluable subjects. If there are 2 or fewer responses among the 20 evaluable subjects, then lenvatinib/everolimus combination therapy will be declared a failure for that disease cohort. Subjects will meet the criteria for being evaluable for an objective response, if they have measurable disease present at baseline and at least 1 postbaseline efficacy assessment, unless they have discontinued prior to the first efficacy assessment due to progressive disease. Participants who are not evaluable for objective response will be replaced.

The Treatment Phase for each subject in Phase 2 ends after completing 4 cycles of treatment unless subject discontinues early. Those subjects who discontinue study treatment before completing 4 cycles transition to the Off-treatment Visit. Those who complete 4 cycles will transition to the Extension Phase. Study treatment and tumor assessments will continue during the Extension Phase.

Dosing Nomogram

The dose nomogram (see Protocol Section 9.1 Table 3) provides the dose of lenvatinib to be administered for BSA increments starting from 0.6 m². BSA must be calculated on Day 1 of each cycle based on the subject's current height and body weight. The actual dose to be

administered is rounded to the nearest whole number. The total lenvatinib dose is capped at 18 mg daily (Dose Levels -1 and 1), and at 24 mg (Dose Levels 2 and 3).

The dose nomogram (see Protocol Section 9.1 Table 4) provides the dose of everolimus to be administered for BSA increments starting from 0.6 m². The total everolimus dose is capped at 5 mg daily for Dose Levels -1, 1, and 2, and at 7 mg daily for Dose Level 3.

Study Duration

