5.4 Primary, Secondary and Exploratory Analyses

5.4.1 Primary Analyses

5.4.1.1 Dose-Finding Analysis in Phase 1

The primary objective of Phase 1 is to determine the MTD and to establish RP2D of lenvatinib administered in combination with everolimus. The study will utilize the rolling 6 design detailed in SAP [Section 3.2](#).

5.4.1.2 Primary Efficacy Analysis for Phase 2

Efficacy analyses for Phase 2 will be performed separately for each study cohort.

The primary objective of Phase 2 is to estimate the antitumor activity of lenvatinib in combination with everolimus in pediatric subjects with Ewing sarcoma/peripheral primitive neuroectodermal tumor (pPNET), rhabdomyosarcoma, and HGG using the ORR at 16 weeks. The ORR at Week 16 is defined as the proportion of subjects who have the BOR of CR or PR at Week 16.

Subjects must have measurable disease present at baseline for Phase 2. Those who have their disease re-evaluated at postbaseline visits will be considered evaluable for objective response. Estimated ORR and its exact 95% CI using the Clopper-Pearson [Clopper and Pearson, 1934] method will be presented.

The data cutoff for the primary study analysis in Phase 2 will occur when all evaluable subjects have completed at least 4 treatment cycles and, if applicable, a confirmatory scan has been performed (in case of a PR or CR at Week 16), or have discontinued study treatment early.

Tumor response data utilized in the primary analysis of ORR will be obtained from investigator's assessment of the imaging scans. No independent tumor assessments will be performed as part of this study. Tumor response will be assessed by RECIST 1.1 criteria [Eisenhauer, et al., 2009] in pediatric subjects with Ewing sarcoma/peripheral primitive neuroectodermal tumor (pPNET) and rhabdomyosarcoma, and RANO criteria will be used for subjects with HGG [Wen, et al., 2010]. Efficacy analyses in Phase 2 will primarily be based on the Evaluable Analysis Set .

The BOR is determined once all data for a subject is known. For this study, a confirmation of CR or PR is required for both RECIST 1.1 and RANO. The confirmation assessments should be made ≥ 4 weeks after the initial response assessment. The BOR is determined by sequentially checking two adjacent assessments (≥ 4 weeks apart).

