13 APPENDICES

13.1 Summary of Efficacy Analyses of Phase 1

Efficacy Variable	Analysis Set	Statistical Method	Tumor Assessments
ORR at data cutoff	Safety Analysis Set	Number (percentage) of subjects (with PR + CR) at data cutoff and its exact 95% CI using method of Clopper and Pearson.	Investigator
DOR	Safety Analysis Set	Median, Q1, and Q3 DOR will be presented (KM method), with 2-sided 95% CIs (Brookmeyer and Crowley, 1982).	Investigator
DCR	Safety Analysis Set	Number (percentage) of subjects (measurable disease with CR + PR + stable disease [SD] ≥ 7 weeks, evaluable disease with CR + Non-CR/Non-PD for RECIST1.1 or IR/SD ≥ 7 weeks for RANO) and its exact 95% CI using method of Clopper and Pearson.	Investigator
CBR	Safety Analysis Set	Number (percentage) of subjects (measurable disease with CR+ PR + SD ≥ 23 weeks, evaluable disease with CR + Non-CR/Non-PD for RECIST1.1 or IR/SD ≥ 23 weeks for RANO) and its exact 95% CI using method of Clopper and Pearson.	Investigator

13.2 Summary of Efficacy Analyses of Phase 2

Efficacy Variable	Analysis Set	Statistical Method	Tumor Assessments
ORR at Week 16	Evaluable Analysis Set	Number (percentage) of subjects (with PR + CR) at Week 16 and its exact 95% CI using method of Clopper and Pearson.	Investigator
ORR at data cutoff	Evaluable Analysis Set	Number (percentage) of subjects (with PR + CR) at data cutoff and its exact 95% CI using method of Clopper and Pearson.	Investigator
DOR	Evaluable Analysis Set	Median, Q1, and Q3 DOR will be presented (KM method), with 2-sided 95% CIs (Brookmeyer and Crowley, 1982).	Investigator
DCR	Evaluable Analysis Set	Number (percentage) of subjects (measurable disease with CR + PR + stable disease [SD] ≥ 7 weeks) and its exact 95% CI using method of Clopper and Pearson.	Investigator
CBR	Evaluable Analysis Set	Number (percentage) of subjects (measurable disease with CR+ PR + SD ≥ 23 weeks) and its exact 95% CI using method of Clopper and Pearson.	Investigator

SIGNATURE PAGE

Author:
 
PPD
 <hr/> 
PPD PPD PPD
 
Oncology, DHBL, Eisai Inc.
	
9/22/2022
 <hr/> 
Date

Approval:
 
PPD
 <hr/> 
PPD PPD PPD
 
Oncology, DHBL, Eisai Ltd.
	
9/22/2022
 <hr/> 
Date

PPD
 <hr/> 
PPD PPD PPD
 
Oncology, DHBL, Eisai Inc.
	
9/26/2022
 <hr/> 
Date

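### Does the two-stage design invalidate the planned Clopper-Pearson interval for the Phase 2 ORR at Week 16?

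*Protocol*

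**What the plan says.** The Phase 2 objective is one of estimation: "To estimate the antitumor activity of lenvatinib in combination with everolimus in pediatric subjects with selected recurrent/refractory solid tumors" (Protocol 8.1), with ORR at Week 16 as the measure.

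The decision rests on response counts in a 10+10 two-stage design. Stage 1: "If there are no responses among the 10 subjects in Stage 1, then the enrollment to that disease cohort will stop for futility" (SAP 3.2); Protocol 9.7.3 repeats it: "At the futility analysis, if there are no responders (CR/PR), then the enrollment for that cohort will be discontinued for lack of efficacy". At the end: "If there are 2 or fewer responses among the 20 evaluable subjects, then lenvatinib/everolimus combination therapy will be declared a failure" (Protocol 9.1). The sample size sections (Protocol 9.7.2, SAP 4) give one-sided alpha 0.07 and 88% power for a 5% null and a 25% alternative.

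The planned summary is the same in four places. The protocol synopsis has "Estimated ORR and its exact 95% confidence interval (CI) using the method of Clopper and Pearson will be presented", Protocol 9.7.1.6.1 has "Estimated ORR and its exact 95% CI using the Clopper-Pearson method will be presented", SAP 5.4.1.2 has "Estimated ORR and its exact 95% CI using the Clopper-Pearson [Clopper and Pearson, 1934] method will be presented", and the Phase 2 table in SAP 13.2 has "at Week 16 and its exact 95% CI using method of Clopper and Pearson". None of them plans a p-value, and none makes the interval a criterion for the conclusion. Protocol 9.7.1 says that endpoints are summarised descriptively.

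**The concern.** Clopper-Pearson treats the number of patients as fixed. Here it is 10 or 20, depending on the data. The sponsor's alpha and power account for that and the interval does not. Three symptoms seem to confirm a fault.

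- The upper limits are out of order: 30.8% after 0/10 but 24.9% after 1/20, although 1/20 is the better outcome. The second excludes the 25% alternative and the first does not.
- In places the upper limit misses the true ORR more often than the nominal 2.5%.
- At 3/20, the smallest result that is not a failure, an ordinary binomial p-value against 5% is 0.0755, above the stated 0.07.

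If the interval undercovered in the range that matters, the main Phase 2 output would be misleading, and a cohort could pass the rule while its reported statistics said otherwise.

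**Working it through.** **Inputs.** Stage sizes 10 and 10, stop at 0/10, failure at 2/20 or fewer (Protocol 9.1, SAP 3.2); null 5%, alternative 25%, one-sided alpha 0.07, power 88% (Protocol 9.7.2); two-sided 95% Clopper-Pearson (Protocol 9.7.1.6.1).

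**Outcome probabilities.** A cohort ends at 0/10 or at x/20 with x = 1 to 20. For true ORR p:

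- P(0/10) = (1−p)^10
- P(x/20) = [C(20,x) − C(10,x)] p^x (1−p)^(20−x), where the subtracted term removes the paths that had no response in stage 1.

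**The plan's own figures.** P(at least 3/20) = 1 − P(0/10) − P(1/20) − P(2/20).

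- At 5%: 1 − 0.5987 − 0.1887 − 0.1440 = 0.0686, stated as 0.07.
- At 25%: 1 − 0.0563 − 0.0106 − 0.0511 = 0.8820, stated as 88%.

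Both reproduce. Without the stage 1 stop they would be 0.0755 and 0.909, so the stated figures do come from the two-stage calculation.

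**The two intervals.** The two-stage exact interval orders the outcomes with 0/10 lowest, then by total responses, and inverts each tail at 2.5%.

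| Outcome | Clopper-Pearson 95% | Two-stage exact 95% | Count rule |
|---|---|---|---|
| 0/10 | 0 to 30.85% | 0 to 30.85% | stop |
| 1/20 | 0.13 to 24.87% | 0.25 to 31.53% | failure |
| 2/20 | 1.23 to 31.70% | 1.42 to 34.31% | failure |
| 3/20 | 3.21 to 37.89% | 3.33 to 38.80% | not a failure |
| 4/20 | 5.73 to 43.66% | 5.80 to 43.95% | not a failure |

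The upper limit moves by 31.53 − 24.87 = 6.7 points at 1/20, by 34.31 − 31.70 = 2.6 at 2/20 and by 38.80 − 37.89 = 0.9 at 3/20. From there the difference shrinks to nothing visible.

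**Coverage under the actual stopping rule.** This is the sum of the outcome probabilities whose interval contains p.

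| True ORR | Clopper-Pearson | Two-stage | Upper-limit miss, Clopper-Pearson |
|---|---|---|---|
| 5% | 98.5% | 98.5% | 0 |
| 10% | 98.9% | 98.9% | 0 |
| 15% | 97.8% | 97.8% | 0 |
| 20% | 99.0% | 99.0% | 0 |
| 25% | 97.6% | 98.6% | 1.06% |
| 30% | 97.9% | 98.3% | 0.34% |

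The zeros follow directly: the lowest of all the upper limits is 24.87%, so none can fall below a smaller true value. At 25% the only miss from above is 1/20, with probability 0.0106. On a grid of step 0.0001 the lowest two-sided coverage is 95.0% (0.949999, at 31.5%), so the nominal level holds to one decimal.

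**The upper tail alone.** It exceeds 2.5% only in narrow bands from 30.8% upward, 4.6 points wide in total. The worst case is 3.96% at a true 31.7%. There the lower tail misses only 0.84%, so two-sided coverage is 100 − 3.96 − 0.84 = 95.2%, and a cohort passes the count rule with probability 96.0%.

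**The order of the upper limits.** The limit after 0/10 rests on 10 patients and the limit after 1/20 on 20. A higher limit from half the data is a matter of precision. As shown, each outcome's interval takes part in valid coverage.

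**The p-value at 3/20.** Fixed-sample: P(Bin(20, 0.05) ≥ 3) = 0.0755. Two-stage: 0.0686. Neither is planned. The 0.07 appears only in the sample size sections, as a property of the count rule, and it is correct there.

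**Would the two-stage 95% interval agree with the count rule?** No. At 3/20 it runs from 3.33% to 38.80% and still contains 5%, as Clopper-Pearson does. Agreement needs the level tied to one-sided 0.07, where the lower limits are 5.04% (two-stage) and 4.84% (fixed-sample).

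**Bias of the raw ORR.** Only the path with no stage 1 response is cut short, so bias = −p(1−p)^10/2. At its largest, p = 9.1%, that is −1.75 points; at 25% it is −0.7.

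**The case for a change.** The best case for a change is that the Phase 2 aim is estimation, so the interval is a main output and should reflect the design that produced it. Two-stage limits rise with the outcome (30.8%, 31.5%, 34.3%), and each tail stays within 2.5%. Outcomes of 1/20 or 2/20, where the limits differ, are not rare: 33.3% of cohorts at a true 5%, 35.3% at 10%, 6.2% at 25%. A reader who sees 3/20 can work out 0.0755 and wonder why the cohort passed. The change would cost a few lines of code.

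The arithmetic stands, and a sponsor who chose the two-stage interval could not be faulted. It does not show that the planned one is wrong. The cohorts where the limits differ are already failures by count. The conflict at 3/20 needs a statistic that nobody plans, and the two-stage 95% interval would leave the similar puzzle of containing 5% for a cohort that passed. A sentence giving the count rule precedence would largely restate Protocol 9.1 and SAP 3.2. Adding a second interval also has a price: two competing 95% intervals on the primary endpoint, an ordering convention to be fixed in advance, and secondary rates (ORR at cutoff, DCR, CBR) that remain on Clopper-Pearson.

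**Conclusion.** The concern does not hold. Under the actual stopping rule the planned interval keeps its two-sided 95% level, to one decimal, at every true ORR. Over the design range of 5% to 25% its upper limit misses at most 1.1% of the time. A two-stage interval would give the same coverage from 5% to 20% at the values checked, one point more at 25%, and limits that differ by more than 0.9 points only for cohorts already declared failures. Alpha (0.0686), power (0.882), sample size and every cohort decision are the same either way.

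This rests on exactly 10 and then 20 evaluable patients, as planned with replacement of non-evaluable subjects, and for the comparison on the ordering given above. Other attained stage sizes would change the individual limits and would need their own enumeration. It also rests on the interval staying descriptive, as the documents have it: a claim that a cohort's ORR exceeds 5% must come from the count rule and not from either 95% interval.
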